4.3 STUDY MATERIALS

4.3.1 LENSES

All study lenses are approved by Health Canada. They will be worn bilaterally and on a daily wear basis. The study lenses are monthly replacement lenses and therefore they will be removed at the end of each day and stored/cared for with OptiFree PureMoist (Alcon).

Table 1: Lens specifications

Lens	Lens A: Biofinity (Coopervision)	Lens B: Total 30 (Alcon)
Material	comfilcon A	lehfilcon A
Device class	3	2
HC licence #	70149	106376
Dk/t (barrer/cm)	160.0	154.0
Sphere power (D)	-0.25 to -6.00 (0.25 steps) -6.50 to -12.00 (0.50 steps) +0.25 to +6.00 (0.25 steps) +6.50 to +8.00 (0.50 steps)	-0.25 to -8.00 (0.25 steps) -8.50 to -12.00 (0.50 steps) +0.25 to +6.00 (0.25 steps) +6.50 to +8.00 (0.50 steps)
Base curve (mm)	8.6	8.4
Diameter	14.0	14.2

4.3.2 LENS CARE SYSTEM

The lens care system to be used by all participants is OptiFree PureMoist. Participants will be provided with sufficient product for the study duration. They will be provided with the package insert and instructed on the (rub and rinse) care procedure as well as on the storage of their study contact lenses.

Table 2: Lens care systems

OptiFree PureMoist	
Manufacturer	Alcon Inc
Health Canada, MDALL	102753

4.3.3 DRUGS

[figure not shown]
Fluorescein will be used to assess ocular health of the anterior ocular surface.

4.3.4 REWETTING DROPS

Participants will not be encouraged to use rewetting drops; however, those who habitually used rewetting drops will be allowed to continue using their normal drops. Rewetting drop use will be recorded at each visit.

4.3.5 ORDERING CONSUMABLES

All study lenses will be provided by CooperVision or sourced from local commercial channels.

4.3.7 CONTACT LENS DISPOSAL

Participants will be instructed to wear the lenses daily and remove at the end of the day to clean/store them in the OptiFree PureMoist provided. All contact lenses worn to each 1-month follow up visit will be collected and stored as per the instructions in section 4.3.6 above. These worn lenses will later be shipped to CooperVision for deposition and surface analysis and subsequent disposal. No genetic materials will be analysed. Unworn lenses may be transferred

to another study or destroyed, according to instructions from CooperVision at the end of the study.

4.3.8 PRODUCT ACCOUNTABILITY

Accountability logs will be kept to include the number of lenses and lens care system bottles received, dispensed, unused and disposed of. All products dispensed to participants will be recorded in the study binder. A manifest will be created for the worn lenses collected, stored and shipped.

4.4 SCHEDULED AND UNSCHEDULED VISITS

This study has a total of 5 study visits, including the screening and exit visits. They are as follows:

- Visit 1: Includes screening, baseline assessments, randomization and fitting of both study lenses
- Visit 2: Randomization & Dispense of study lens Pair #1 (this will be combined with Visit 1 if all eligibility criteria met at V1)
- Visit 3: 1-month follow up of study Pair #1, dispense of study Pair #2
- Visit 4: 1-month follow up of study Pair #2
- EXIT: Typically occurring immediately after Visit 4 unless participant discontinues early

The scheduled follow-up visits 3 and 4 may only take place when the participant attends wearing the study lenses for a minimum of 6 hours. If this is not the case, and the participant is not experiencing any problems with the lenses, the appointment will be rescheduled, ideally within the visit window.

Visits that fall outside of the specified visit windows will be designated as protocol deviations and at the end of the study, the data collected during protocol deviations will be assessed for their suitability to be included in the analysis population.

4.4.1 SCREENING

The investigator will determine participant eligibility at Visit 1 using the inclusion and exclusion criteria. Participants will be assigned a study ID number after they sign the consent documentation process, i.e. before their eligibility for the study has been confirmed. Ineligible participants will be discontinued from the study.

4.4.2 REPEATED SCREENING

In some circumstances a repeated screening may need to be scheduled. Examples include, but are not limited to:

1. Incomplete information available at time of screening to determine eligibility (e.g. current lens brands worn, history from current eye care practitioner etc.)
2. Study procedures unable to be completed in time scheduled for visit;
3. Study products not available at the time of the screening visit;
4. A transient health condition which may affect the eye(s) (e.g. a common cold, active allergies, fatigue etc;)
5. The short term use of medications (e.g. antibiotics, antihistamines etc.)
6. Reassessment of baseline ocular conditions (e.g. corneal and/or conjunctival staining, scars etc.)

Two repeat screenings are allowed, i.e. the maximum number of screenings permitted will be 3.

4.4.3 SCHEDULED STUDY VISITS

Table 3 below summarises the scheduled visits, including their visit code number, estimated duration and the day count or visit window.

Table 3: Summary of visits

Visit code	Visits	Duration (hours)	Day/Visit window
V1	Screening and fitting	1.0	0
V1/R1	1 st repeat of V1 if needed	As needed	0
V1/R2	2 nd repeat of V1 if needed	As needed	0
V2	Dispensing & masking 1 st study lens, same day as V1 (or V1/R1 or V1/R2)	0.75	0
V3	1-month follow up for 1 st study lens, dispensing & masking 2 nd study lens	1.25	Day 28, 29, 30 or 31 from V2 (where Visit 2 = Day 0). Pair 2 dispensing = Day 0
V4	1-month follow up for 2 nd study lens	0.75	Day 28, 29, 30 or 31 from V3 (where Visit 3 = Day 0).
EXIT	Anticipated to follow immediately after V4 unless participant discontinues early	0.25	n/a
US-1	1 st Unscheduled visit	As needed	n/a

4.4.4 UNSCHEDULED VISITS

An unscheduled visit is defined as an interim visit requested by the participant or investigator due to an unanticipated problem. Data recorded at these visits will be entered into the database. Only relevant and applicable unscheduled visit information will be included in the final report as deemed necessary by the lead investigator.

4.5 STUDY PROCEDURES

A summary of the study procedures to be conducted at scheduled visits is listed in Table 4. More procedure details are included for each visit in the following sections.

Table 4: Summary of procedures to be conducted at scheduled visits

	V1 Screen Fit of study CL	V2 Dispense first study lens	V3 1-month follow- up first study lens, dispense second study lens	V4 1-month follow- up second study lens	Exit
Consent process	X				
Subject age & sex	X				
CL history (brand & power) [^] and lens wear schedule	X		X	X	
Health & medication	X	X	X	X	
Review any problems with eyes/study lenses		X	X	X	
	X				X (OR SUBJ. REFRACTION)
	X				
	X				
Randomization		X			
	X				
Dispense study CLs		X	X		
	X	X	X	X	
	X	X	X	X	
		X	X	X	
			X	X	
		X	X		
			X	X	
	X	X*	X	X	X*
Study CL collection			X	X	
Study completion and Exit					X

4.5.1 VISIT 1 SCREENING AND FIT VISIT

Informed consent shall be obtained in writing from the participant and the process shall be documented before any procedure specific to the clinical investigation is carried out. Participants will be assigned a study ID after they sign the consent documentation, i.e. before their eligibility for the study has been confirmed.

The investigator will determine participant eligibility using the inclusion and exclusion criteria. Ineligible participants will be discontinued from the study.

The study procedures to be conducted at this visit are detailed below:

1. The participant is expected to attend the screening / baseline visit wearing either their habitual contact lenses or spectacles.
2. The participant will be required to read and sign an Informed Consent Form prior to enrollment. When the participant has signed the consent form, the participant will be considered enrolled in the study.
3. Participant demographics and medical history (age, sex, medical conditions, medications, allergies).
4. Contact lens history (habitual lens information and wearing habits).
5. [REDACTED]
6. The participant removes their habitual contact lenses (if applicable).

7. [REDACTED]
- [REDACTED]

c. [REDACTED]
[REDACTED]
[REDACTED]
[REDACTED]
[REDACTED]
[REDACTED]
[REDACTED]

12. Trial fitting of both study lenses. For logistical purposes to ensure the appropriate fitting for each lens type, the study investigator will not be masked during the trial fitting of the lenses.

a. [REDACTED]
[REDACTED]
[REDACTED].

- b. The contact lenses will be provided to participants in a manner that does not unmask the participant as described in Section 4.1.3.
- c. The participant will insert the lenses.

d. [REDACTED]
[REDACTED]
[REDACTED]
[REDACTED]
[REDACTED]
[REDACTED]
[REDACTED]

13. The investigator will confirm that the participant meets the eligibility specifications set out in the inclusion criteria and exclusion criteria and is eligible to continue in the study.

14. [REDACTED]
[REDACTED]

4.5.2 VISIT 2 DISPENSE PAIR # 1

This visit may or may not be immediately subsequent to the screening visit, depending on lens availability but will occur no later than 30 days after Visit 1.

The study procedures are outlined below:

1. If this visit does not immediately follow V1, then confirm health and adverse event status.

2. [REDACTED]

[REDACTED]

[REDACTED]

[REDACTED]

[REDACTED]

[REDACTED]

[REDACTED]

3. The participant will be assigned a randomization number (Randomization ID#) by the unmasked research assistant.

4. The first pair (lens pair #1) of study contact lenses (either Lens A or Lens B) will be selected by the unmasked research assistant according to the randomization table.

5. Lens pair #1 will be provided to participants in a manner which does not unmask the participant or investigator, as described in Section 4.1.3.

6. The participant will insert the lenses.

7. The contact lenses will be allowed to settle for 5 minutes.

8. [REDACTED]

c) [REDACTED]
[REDACTED]
[REDACTED]
[REDACTED]
[REDACTED]
[REDACTED]
[REDACTED]
[REDACTED]

11. The participant will be asked to wear the study lenses for at least 8 hours per day and 6 days per week.

12. [REDACTED]
[REDACTED]

13. The participant will be provided with instructions for the safe wear & care of the contact lenses as well as sufficient care product supply.

14. [REDACTED]
[REDACTED]
[REDACTED]

4.5.3 VISIT 3 1-MONTH FOLLOW-UP PAIR #1 & DISPENSE PAIR #2

Participants will be asked to attend this visit after wearing Lens Pair #1 for at least 6 hours. This visit will occur 28-31 days (inclusive) after visit 2.

[figure not shown]
The study procedures are outlined below:

1. Review changes to medical history and medications.
2. The participant will be asked to score their subjective responses and rate their typical wearing schedule and reflect on their overall satisfaction [REDACTED]
[REDACTED] during the month for the lens performance items listed below:

a) [REDACTED]
[REDACTED]
[REDACTED]

d) Overall satisfaction with handling for lens removal (0 – 10 scale, 0.5 steps);

e) [REDACTED]
[REDACTED]
[REDACTED]

4.5.4 VISIT 4 1-MONTH FOLLOW-UP PAIR #2

Participants will be asked to attend this visit after wearing Lens Pair #2 for at least 6 hours. This visit will occur 28-31 days (inclusive) after visit 3.

The study procedures are outlined below:

1. The same procedures will be carried out for study lens #2 as described in Section 4.5.3
1-MONTH FOLLOW-UP OF LENS TYPE #1 (VISIT 3), points 1 to 8.
2. [REDACTED]
- [REDACTED]
- [REDACTED]

4.5.5 EXIT VISIT

The study exit form will be completed when a participant exits the study. This form will be completed either at study completion, or if the participant is discontinued from the study at another time. A study exit form must be completed for all participants who have taken a study ID number. If in the opinion of the investigator post-study follow-up visits are required, the exit form will be completed after the last follow-up visit.

[REDACTED]

[REDACTED]

[REDACTED].

After the exit assessments have been completed, the participant and investigator will complete the study completion and remuneration forms. At this time the participant will be considered as having exited the study.

5 MONITORING PROTOCOL ADHERENCE

Adherence to study visit windows, lens wearing schedule, and time windows around other data collection points (i.e. subjective ratings) will be monitored internally by CORE. Deviations from the study plan as described in the protocol will be reported in the study report. As described in Section 13.4.3, major protocol deviations will be reported to the Sponsor and the University of Waterloo's Office of Research Ethics (ORE) within 7 days of becoming aware of them (as per ORE's guidelines).

6 POTENTIAL RISKS AND BENEFITS TO HUMAN PARTICIPANTS

This is a minimal risk study because of the use of approved products and standard optometric assessments.

Contact lenses in this study will be worn according to their approved use ie. worn daily on a monthly replacement schedule, and participants will be asked to wear them for a minimum of 6 days a week, 8 hours a day. Adverse events and/ or complications in daily wear of soft contact lenses can occur (eg: inflammation and infection). When contact lenses are worn on a daily wear basis, there is a small risk of an adverse event compared to not wearing contact lenses. When contact lenses are worn on an extended wear basis, there is a significantly increased risk of an

adverse reaction compared with wearing contact lenses on a daily wear basis. Participants in this study will be instructed to remove and clean the lenses at the end of each day, using the products and lens case provided.

Additionally, it is possible that participants may experience temporary discomfort associated with the study procedures and contact lens wear including: burning and stinging, blurred vision, sandiness or grittiness, light sensitivity, dryness, itching, crusty eyes and foreign body sensation.

Parts or all of this study will be conducted during the COVID-19 pandemic. Therefore, risks of infection with COVID-19 exist through participation. These risks arise due to possible exposure during commute to and from the study visit as well as during the study visit, particularly due to the closeness of the investigator and participant (within 2m for some assessments). The potential effects of COVID-19 are not yet fully known and may include long-term health consequences. In a small percentage, infection with COVID-19 can lead to serious illness, hospitalization, and in rare cases to complications leading to death. Individuals aged 60 and above and those with underlying medical conditions are considered at a greater risk for severe illness from the COVID-19 virus.

In consideration of risks associated with COVID-19, CORE has implemented a series of on-site safety procedures which have been reviewed and approved by the University of Waterloo. These include, but are not limited to, self-screening of investigators and participants prior to entering the building, maintaining physical distancing as much as possible, frequent handwashing, wearing of face masks by the investigator and participant, and frequent room and equipment hygiene and decontamination. In addition, members of CORE and participants follow the University policies regarding Covid-19 vaccination.

Participants will not benefit directly from taking part in this study. Information from this study may help researchers come up with new soft contact lens designs to help others in the future. This study may help the study sponsor to better understand the performance of the products being used in this study.

7 ADVERSE EVENTS

See CORE SOP012 AE Reporting for a description of the reporting of adverse events, including management and reporting. An 'adverse event' refers to any undesirable clinical occurrence in a participant, whether it is considered to be device-related or not. Adverse events (AE) may be classified as 'unanticipated adverse device effects', 'serious adverse events', 'significant adverse

events', or 'non-significant adverse events' as defined below in Table 5: Classification of types of adverse event.

A number of conditions may result in temporary suspension until resolution. These include corneal infiltrates, corneal staining, limbal injection, bulbar injection or tarsal conjunctival abnormalities.

Table 5: Classification of types of adverse event

Classification	Definition
Serious Adverse Event	Those events that are life-threatening, or result in permanent impairment of a body function, or permanent damage to a body structure or necessitate medical (therapeutic) or surgical intervention to preclude permanent impairment of a body function or permanent damage to a body structure.
Significant Adverse Event	Those non-serious adverse events that occur with contact lens usage that are not sight-threatening but are usually symptomatic and may warrant therapeutic management and /or temporary or permanent discontinuation of contact lens wear.
Non-Significant Adverse Events	Those less severe non-serious adverse events that occur with contact lens usage that are not sight-threatening, may or may not be symptomatic and may warrant palliative management, such as ocular lubricants or temporary interruption of contact lens wear.
Unanticipated Adverse Device Effect	Adverse events in a study that were not previously identified in the protocol in terms of nature, severity, or degree of incidence. An Unanticipated Serious Adverse Device Effect is an unanticipated adverse event that is serious in nature and caused by or associated with the device and is considered reportable.

AE classification, coding (for reporting to the sponsor) and reporting details, plus examples, are provided in Table 6.

Table 6: Contact lens adverse event classification, coding and reporting guide

Code	Condition	Reporting
Serious Adverse Events		
01	Presumed infectious keratitis or infectious corneal ulcer	For all serious AEs: Notify sponsor as soon as possible, within 24 hours ; ORE reporting will be within 24 hours as per requirements
02	Permanent loss of ≥ 2 lines of best spectacle corrected visual acuity (BSCVA)	
03	Corneal injury that results in permanent opacification within central cornea (6mm)	
04	Uveitis or Iritis (e.g. presence of anterior segment inflammation as described in ISO 11980, Annex B)	
05	Endophthalmitis	
06	Hyphema	

07	Hypopyon	
08	Neovascularization within the central 6mm of cornea	
00	Other serious event	
Significant Adverse Events		
11	Peripheral (outside central 6mm), non-progressive, non-infectious ulcer	
12	Symptomatic corneal infiltrative event	
13	Superior epithelial arcuate lesions (SEALs) involving epithelial split	
14	Corneal staining \geq dense coalescent staining up to 2mm in diameter (e.g. moderate, ISO 11980 grade 3)	
15	Corneal neovascularization \geq 1.0mm vessel penetration (e.g. \geq ISO 11980 Grade 2), if 2 grade change from baseline	
16	Any temporary loss of \geq 2 lines BSCVA for \geq 2wks	
17	Any sign and/or symptom for which participant is administered therapeutic treatment or which necessitates discontinuation of lens wear for \geq 2 weeks	
10	Other significant event	
Non-significant Adverse Events		
21	Conjunctivitis (bacterial, viral or allergic)	
22	Papillary conjunctivitis if \geq mild scattered papillae/follicles approximately 1mm in diameter (e.g. ISO 11890 Grade 2), if 2 grade change from baseline	
23	Asymptomatic corneal infiltrative events	
24	Any sign and/or symptom for which temporary lens discontinuation for $>$ 1 day is recommended (if not already classified)	
20	Other sign and/or symptom warranting classification as a non-significant adverse event	

8 DISCONTINUATION FROM THE STUDY

Participants may be discontinued at the discretion of the investigator or sponsor in consideration of participant safety or protocol compliance, or at discretion of the participant. Participants discontinued from a study will be reimbursed \$20 per hour for their active involvement in the study (including the initial screening visit). Upon discontinuing, a participant will be offered the

option of their data being withdrawn from future statistical analysis. The following is a list of possible reasons for discontinuation from the study:

- Screening failure: Participants will be discontinued if they do not meet the inclusion and exclusion criteria outlined in section 4.2.3.
- Unacceptable performance with products to be used in study: Participants may be discontinued if they are unable to achieve acceptable comfort and /or vision with the study products.
- Positive slit lamp finding: Participants may be permanently discontinued from the study depending on the severity of the condition and on the judgement of the investigator.
- Adverse event: If a participant experiences an adverse event during the study they may be discontinued based on the clinical judgement of the investigator.
- Symptoms: If the participant has persistent symptoms they may be discontinued based on the clinical judgement of the investigator.
- Disinterest, relocation or illness: The participant may choose to discontinue due to reasons within or beyond their control.
- Violation of protocol or non-compliance: The participant will be discontinued if they are unable or unwilling to follow the protocol specified visit schedules and/or study procedures.
- Instillation of topical ocular medication: The participant will be discontinued if they elect to use a topical ocular medication during the study unless that topical ocular medication is prescribed for a limited duration (less than two weeks) to treat a transient condition; in this case the participant may remain an active participant (at the discretion of the investigator) after stopping topical ocular medication following resolution of the ocular condition).
- Lost to follow-up: The participant will be discontinued if they cannot be contacted and do not return for a final exit visit, and if the investigator has made a reasonable effort to contact the participant for a final study visit.
- Premature termination of the study by the sponsor, CORE or the Office of Research Ethics at the University of Waterloo.

A discontinuation form, stating the reason for discontinuation will be completed, which requires the signatures of both the participant and the investigator except where the participant is lost to follow-up in which case only the signature of the investigator is required.

All discontinuations including their reasons will be included in the final report.

9 STUDY COMPLETION AND REMUNERATION

At the last scheduled protocol visit a study completion form will be completed, which requires the signatures of both the participant and the investigator. The participants will also be provided with a letter of appreciation. This letter provides information on how to seek the study results when the study is completed.

After signing the completion forms, participant remuneration will be provided in the form of a cheque and documentation will be signed to confirm receipt. Remuneration will be calculated at a rate of \$20 per visit hour (including the initial screening visit). Full details are given in the information consent letter.

10 STATISTICAL ANALYSIS AND DATA MANAGEMENT

10.1 STATISTICAL ANALYSIS

Primary comparisons will be between study lenses (e.g. in-office subjective ratings of lens handling collected after 1 month).

All data will be analyzed by CORE at the University of Waterloo. Unmasked data analysis will be conducted using Statistica, SPSS or other appropriate software. Descriptive statistics will be provided on information regarding baseline variables (age, gender, refractive error distribution, etc.).

Table 7 lists the primary outcome variables and anticipated statistical procedures.

Table 7: Statistical procedures

Variable	Analysis	Statistical test
Subjective ratings	Descriptive and other statistics	Mean, Median*, Standard Deviation, Minimum, Maximum, Frequency count
	Effect of treatment on outcome variable within subjects (comparison between study days)	Wilcoxon matched pairs test
		Mean, Median*, Standard Deviation, Minimum, Maximum, Frequency count
		Wilcoxon matched pairs test

The critical alpha level for statistical significance will be set at 0.05, with no adjustments for multiple comparisons.

All participants who were evaluated will be included in the analysis, unless their removal is agreed by the sponsor due to protocol deviations and/or adverse events. In the event of missing data, individual data points will not extrapolated from the collected data.

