4 MATERIALS AND METHODS

4.1 STUDY DESIGN

4.1.1 OVERALL DESIGN

This study will be a prospective, randomized, double-masked, single-site, 1-month cross-over design involving bilateral eye daily wear of two different monthly replacement CL types. Each lens will be worn bilaterally for approximately one month.

There are 5 scheduled study visits that take place on 3 different days, including the screening and exit visits:

Visit 1: Screening/eligibility, baseline assessments and fitting of both study lenses

Visit 2: Subject randomization and Dispense of study lens Pair #1 (this will be combined with Visit 1 if participant meets all eligibility criteria at V1)

Visit 3: 1-month follow up of study Pair #1, dispense of study Pair #2

- [REDACTED] 1

Visit 4: 1-month follow up of study Pair #2, and study exit

- [REDACTED]

EXIT: Anticipated to follow immediately after Visit 4 unless participant discontinues early

[REDACTED]
[REDACTED]

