4.1.2 RANDOMIZATION

A randomization schedule will determine the order of wear of lens A and lens B for the first and second month, for each participant. Participants will be randomized at the beginning of Visit 2 after eligibility has been confirmed during V1.

A randomization schedule will be generated by CORE's data management team and provided to the unmasked research assistant(s) for the study. It will be included in the final report. Study investigators will remain masked to the randomization schedule until the study is completed and the database is locked.

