4.2 STUDY POPULATION

4.2.1 SAMPLE SIZE CALCULATION

The sample size was calculated using data of 'lens handling at removal' ratings collected in a previous study using a 0-10 rating scale. This data showed a standard deviation of paired differences of 1.02. With an alpha level of 0.05 in a paired difference test, and power of 84%, a minimum sample size of 20 participants is recommended in order to determine a statistically significant difference of 0.71 between study lenses , Figure 1.

To account for dropout, up to 25 participants may be randomized and dispensed with study product in total, with the target of at least 20 completing the study.

[figure not shown]

Figure 1: Sample size calculation graph

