4.2.3 INCLUSION AND EXCLUSION CRITERIA

A person is eligible for inclusion in the study if he/she:

1. Is at least 17 years of age and has full legal capacity to volunteer;
2. Self-reports having had a full eye examination within the previous 2 years;
3. Has read and signed an information consent letter;
4. Is willing and able to follow instructions and maintain the appointment schedule;
5. Is a habitual wearer of frequent replacement contact lenses;
6. Anticipates no difficulty wearing the contact lenses for 6 days/week and 8 hours/day during the study;
7. Has refractive astigmatism no higher than -0.75DC in each eye;
8. Can be successfully fit with both study lens types;
9. Achieves at least 0.4 logMAR VA monocularly and at least 0.2 logMAR VA binocularly with each study lens type.

A person will be excluded from the study if he/she:

1. Is participating in any concurrent clinical research study;
2. Has any known active* ocular disease and/or infection;
3. Has an unstable systemic condition that in the opinion of the investigator may affect vision or contact lens comfort across the 2-month study duration;
4. Is using any systemic or topical medications in an irregular routine that in the opinion of the investigator may affect vision or contact lens comfort across the 2-month study duration;
5. Has known sensitivity to the diagnostic sodium fluorescein to be used in the study;
6. Is an employee of the Centre for Ocular Research & Education.

* For the purposes of this study, active ocular disease is defined as infection or inflammation which requires therapeutic treatment. Mild (i.e. not considered clinically relevant) lid abnormalities (blepharitis, meibomian gland dysfunction, papillae), corneal and conjunctival staining and mild dry eye are not considered active ocular disease. Neovascularization and

corneal scars are the result of previous hypoxia, infection or inflammation and are therefore not active.

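### The legible lens comparison is a Wilcoxon matched pairs test that ignores the randomised wear order; a prespecified period-adjusted comparison alongside it would be a cheap improvement, not the repair of an invalid test.

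*Combined protocol and SAP*

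**What the plan says.** Section 4.1.1 describes a "1-month cross-over design involving bilateral eye daily wear of two different monthly replacement CL types". Section 4.1.2 makes the order of wear the randomised factor: "A randomization schedule will determine the order of wear of lens A and lens B for the first and second month, for each participant". It states neither an allocation ratio nor blocking.

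Section 10.1 says that "Primary comparisons will be between study lenses". For the subjective ratings, which include the primary outcome (handling on removal at 1 month, 0-10 in half-point steps), the legible part of Table 7 gives descriptive statistics and a "Wilcoxon matched pairs test". The row describes the comparison in terms of study days. No legible text mentions a period, sequence or order term.

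Section 4.2.1 sizes the trial on a paired difference test: "This data showed a standard deviation of paired differences of 1.02", with 20 completers, a difference of 0.71, alpha 0.05 and 84% power. It adds that "up to 25 participants may be randomized and dispensed with study product in total, with the target of at least 20 completing the study".

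**The concern.** In a two-period crossover, each participant's B minus A difference contains the lens effect plus or minus any change in ratings between the two months. The sign depends on which lens came first. A matched pairs test pools all differences without regard to order, so the shift stays in them.

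Two consequences follow. If the orders are equally represented among completers, the shift cancels on average but inflates the spread, so power falls. If they are not, part of the shift also remains in the estimated lens difference. Both can be removed with information that the design already collects. Section 10.1 describes the analysis as unmasked ("Unmasked data analysis will be conducted using Statistica, SPSS or other appropriate software"), so a decision to adjust made after seeing the data would be open to question. It is better fixed in advance.

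**Working it through.** **Inputs.** From section 4.2.1: N = 20 completers, difference 0.71, SD of paired differences 1.02, alpha 0.05, up to 25 randomised. Assumed, because the documents do not give it: a month 2 minus month 1 shift p of 0, 0.1, 0.25 or 0.5 points. Sidedness is not stated.

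**The plan's own figure.** Two-sided paired t, 19 df, noncentrality 0.71 × √20 / 1.02 = 3.11, gives 83.95%. The stated 84% reproduces. A one-sided t gives 91.2% and a normal approximation 87.6%, so a two-sided t is evidently what was used.

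**Model.** B − A has mean 0.71 + p in order AB and 0.71 − p in order BA. Let n1 and n2 be the completers in AB and BA.

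- Unadjusted mean difference: 0.71 + p(n1 − n2)/N.
- Expected variance of the pooled differences at 10/10: 1.02² + p² × 20/19.
- Adjusted estimate: the average of the two order-specific means. Its SE is (1.02/2) × √(1/n1 + 1/n2), with N − 2 = 18 df.

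**Equal orders (10/10), 1.02 taken as the within-order SD.** The pooled variance is 1.0404 + 0.0658 = 1.106 at p = 0.25 and 1.0404 + 0.2632 = 1.304 at p = 0.5. In variance terms the 20 pairs are worth 20 × 1.0404/1.106 = 18.8 and 20 × 1.0404/1.304 = 16.0 pairs. Power from 200,000 simulated trials per setting, with normal differences:

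| Shift | Paired t | Planned Wilcoxon | Period-adjusted t |
|---|---|---|---|
| 0 | 84.0% | 82.1% | 83.8% |
| 0.1 | 83.8% | 81.9% | 83.9% |
| 0.25 | 82.4% | 80.3% | 83.8% |
| 0.5 | 77.3% | 74.5% | 83.7% |

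The noncentral t value for the adjusted test is 83.73% at every shift, so its cost at no shift is 83.95 − 83.73 = 0.2 points against a paired t. About 2 points of the gap between the Wilcoxon and the adjusted t is rank test versus t test, not period.

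**If 1.02 already contains period variation.** The within-order SD is then √(1.02² − p²). Paired t power is 84.1, 84.0, 84.7 and 86.6% across the four shifts, and adjusted t power is 83.9, 84.1, 86.1 and 92.2%. Nothing is lost against the plan; adjustment can only add once there is a material shift.

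**Unequal orders (12/8).** The bias is p × 4/20: 0.02, 0.05 and 0.10 at shifts of 0.1, 0.25 and 0.5. Depending on the direction of the shift, Wilcoxon power is 84 or 80%, 86 or 74%, and 86 or 61%; the higher figure in each pair comes from the bias. The adjusted SE is 0.51 × √(1/12 + 1/8) = 0.233, which gives 82.2% power at any shift.

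**How likely is 12/8 or worse?** With a 13/12 schedule and 5 of 25 lost at random, it happens if 0, 1 or 5 of the losses come from the group of 13: (792 + 6,435 + 1,287)/53,130 = 16%. With unblocked allocation of 20 completers it is 50%.

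**Type I error of the Wilcoxon.** At shift 0.25: 4.3% (10/10), 4.7% (12/8), 5.3% (13/7). At 0.5: 2.9, 4.3 and 6.3%. Averaged over allocation at 0.5: 3.3% (13/12 schedule) or 4.8% (unblocked).

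**Sensitivity to the distribution (10/10).**

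- Ratings rounded to half points and capped at 0-10, between-participant SD 1.0 assumed: type I error of the adjusted model is 4.8-5.1%. Its power at no shift is 82.0% with a Lens A mean of 7 (paired t 82.4%) and 79.8% with a mean of 8 (paired t 80.2%).
- Half-step differences with t-4 tails (assumed): adjusted t against Wilcoxon is 84.8 v 88.3% at no shift, 84.1 v 86.2% at 0.25 and 84.6 v 84.3% at 0.4. With t-5 tails it is 84.0 v 86.2% at no shift and 84.2 v 84.8% at 0.25.
- A rank-sum test on period differences, under normality: 79.8% against 82.1% for the Wilcoxon at no shift, and 79.7% against 79.5% at 0.3.

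**The case against.** The harm is hypothetical. No period shift is documented, and the inclusion criteria ask that each participant "Is a habitual wearer of frequent replacement contact lenses", so nothing in the text supports a large practice effect in handling. A shift of 0.5 would be 70% of the 0.71 target (0.5/0.71). At 0.1 adjustment gains nothing material, and at 0.25 it gains 1.4 points against a paired t. This stands, and it limits the point to an improvement.

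A rank test is also a defensible choice for a bounded half-step scale, and replacing it with a normal-theory model is a separate decision from adding a period term. That stands too: under moderately heavy tails the Wilcoxon is ahead until the shift reaches about 0.3 to 0.4, and the documents give no distribution for the ratings.

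A reader might infer that adjustment pays once the shift exceeds about 0.1 points. That break-even (0.094) compares an adjusted t with a paired t, and the planned test is neither. A reader might also infer that the primary result would be biased or its type I error inflated. With equal orders there is no bias. With unequal orders the bias is conditional on the realised split, and averaged over allocation the error rate is not inflated.

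Finally, parts of Table 7 are not legible and its procedures are described as anticipated, so the statement that order is not used covers the legible text only.

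**Conclusion.** The point holds as an efficiency and prespecification matter. The legible plan leaves the randomised order unused, so any month 1 to month 2 shift remains in the lens differences. Relative to a paired t at 10/10, the loss is nil at small shifts, 1.4 points of power at 0.25 and 6.4 at 0.5. At 12/8 the conditional bias is one fifth of the shift. These figures rest on 20 complete pairs, normal differences, an assumed shift and 1.02 being the within-order SD. If 1.02 already includes period variation, there is no shortfall against the planned power.

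The documents do not support calling the Wilcoxon test invalid, nor claiming that an adjusted t would beat it whatever the distribution of the ratings.

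**What to change.** In section 10.1 and Table 7, prespecify a Lens A versus Lens B comparison adjusted for period, among participants with ratings in both periods. The estimate is the average of the two order-specific mean B − A differences. This is equivalent to a linear model with lens, period and participant, on N − 2 degrees of freedom. Report it with a 95% CI alongside the Wilcoxon matched pairs test, and state before unmasking which of the two is primary. It would also help if section 4.1.2 said whether the order schedule is balanced, since that drives the chance of unequal orders.

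The cost is wording and one standard model; section 10.1 already leaves the software open. The plan should acknowledge these downsides:

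- **Against a paired t:** 0.2 points of power if balanced with no shift; at 12/8 the adjusted power is 82.2%.
- **Against the planned Wilcoxon:** the adjusted t is ahead at 10/10 under normal differences, but about 2 to 4 points behind at no shift if differences are heavy-tailed.
- **If a rank method is preferred for the adjusted analysis:** a rank-sum test on period differences costs about 2 points at no shift and overtakes the Wilcoxon only at a shift of about 0.3.
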